4.3 Treatment assignment and randomization

All eligible patients will be randomized to one of three arms: 1) “why” messaging, 2) “how” messaging, or 3) “standard of care (“usual care”). We plan to conduct stratified randomization based on the primary care clinic the patient attends to account for differences in patient populations between clinics. We will also use block-stratified randomization, in which the unit of randomization is the day of the week the study visit is on. This choice was made in response to the logistical difficulties randomizing at the patient level presented. Each weekday, eligible patients will be identified that have an upcoming visit 2-3 days from then. The day of the week of that visit will be randomized in a 1:1:1 ratio with a random number generator to one of three arms: 1) “why” messaging, 2) “how” messaging or 3) “standard of care” (“usual care”).

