5.2 Overall Design

We will use the Mass General Brigham COVID-19 Vaccine Registry and EHR information in the Research Patient Data Registry (RPDR) and/or Epic Enterprise Data Warehouse (EDW) to identify all patients age ≥ 18 with an upcoming primary care outpatient appointment who are eligible for the COVID booster vaccine. We plan to launch the study after the booster vaccine has become widely available to adults over age 18 and supply of vaccines at MGB is anticipated to be sufficient. All eligible patients will be randomized to one of three arms: 1) “why” messaging, 2) “how” messaging, or 3) standard of care (“usual care”). We will conduct stratified randomization based on the primary care clinic the patient attends and day of the week the upcoming visit is on.

The primary outcome will be the rate of booster vaccination at the targeted visit. Secondary outcome will be receipt of a booster vaccine within 6 weeks of the target visit at any location. After completion of the trial, we will utilize data from the RPDR and/or EDW to develop models that predict which patients are most likely to respond to each intervention using patient baseline characteristics, which in the future could allow for targeting of interventions to specific patients. We will use the Mass General Brigham COVID-19 Vaccine Registry and the RPDR/EDW for outcome measurement.

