5.2.1 Aim 1 Design

[figure not shown]
In Aim 1 of the study, we will conduct a 3-arm randomized controlled trial to compare the effectiveness of two interventions compared to usual care on COVID-19 vaccination uptake. We will include Mass General Brigham (MGB) patients age ≥ 18 with an upcoming primary care outpatient visit with a Mass General Hospital primary care provider who are eligible for the COVID booster vaccine and who have not received a dose. This approach has been approved by MGH primary care leadership. Patients will be excluded if they did not receive the full set of their primary COVID-19 series.

Patients will be randomized equally to one of three arms: 1) “why” messaging, 2) “how” messaging, or 3) standard of care (“usual care”). We plan to conduct stratified randomization based on the primary care clinic the patient attends to account for differences in patient populations between clinics and based on the day of the week the upcoming visit is on to minimize logistic difficulties in the intervention delivery. “Why” messages will focus on reasons to get the vaccine, including protecting self and loved ones or the idea of herd immunity. “How” messages will focus on the details of obtaining a vaccination at MGB, what to expect, and how to prepare for the visit. The messages will be sent through the EHR electronic patient portal for portal users. For patients whose primary language listed in the EHR is not English, they will be offered translated messages following standard MGB Gateway messaging practices. Gateway messages will first include a message translated in their primary language (Spanish, Portuguese, Arabic, Chinese, Russian, Haitian Creole or Bosnian) followed by an English version of the message. Consistent with recent studies for influenza vaccination and the approach approved by MGH primary care leadership, we will send a message to patients a few days in advance of their office visit.¹⁶ Based on current MGH practice (i.e., standard of care), patients in Arm 3 will not receive any additional message about their upcoming visit, beyond what they already receive by MGH. **Initial examples of these messages are attached.**

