5.6 End-of-study definition

The active interventions in Aim 1 are expected to last no more than 1 week. The study data collection of vaccination receipt will begin after the target primary care outpatient visit will conclude 1 month after the target visit is complete, as we anticipate some lag for complete vaccination information to be included in the MGB COVID-19 Vaccine Registry data source. Development of the prediction models will be done following Aim 1 data collection.

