6.4 Samples size determination

Sample size estimates suggest that ~1,100 individuals in each arm will allow us to observe a 5% difference in vaccination rates compared to the usual care arm, assuming a usual care arm vaccination rate of 20% as well as assumptions of alpha=0.05 and power=0.80. Given that more than 1 million patients receive care at MGB, we expect to identify at least 5,000 patients who have not yet received the booster vaccination at the outset of the trial and who will be eligible to receive one of the messages. This will also provide sufficient power for secondary outcomes. Under the same assumptions, we should be able to observe a <6% difference in 6-week vaccination rates compared to usual care, assuming a usual care arm vaccination rate of 25%.

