6.5 Statistical analyses

6.5.1 Analysis of the primary endpoint

The primary outcome will be the rate of receipt of COVID booster vaccine dose in each arm at the target primary care outpatient appointment, treated as a binary outcome. We will use logistic regression to compare outcomes between each intervention arm versus usual care and against each other. Of note, we chose not to formally adjust for multiple testing in the primary analysis for several reasons. First, although the chance of finding at least one false positive among several tests is >5%, a Bonferroni correction would be much too conservative in this case, because the multiple comparisons among the treatment arms share the same four exposure groups. Second, a recent systematic review of multiple arm trials showed that more than half of all randomized trials with multiple exposure groups do not adjust for multiple comparisons,¹⁸ reasoning that if each exposure was compared with control in a separate trial, no adjustment would be necessary.

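### Visit days rather than patients are randomised, but the sample size and the logistic regressions treat patients as independent; if same-day outcomes correlate, the false-positive rate exceeds 5%

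*Combined protocol and SAP*

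**What the plan says.** Section 4.3 gives the unit of allocation directly: "the unit of randomization is the day of the week the study visit is on". It explains that patient-level allocation was logistically difficult and adds: "The day of the week of that visit will be randomized in a 1:1:1 ratio with a random number generator". The same section also stratifies by primary care clinic.

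Other sections describe the design differently. Section 5.2 treats the day as a stratum: "We will conduct stratified randomization based on the primary care clinic the patient attends and day of the week the upcoming visit is on". Section 5.2.1 says that patients are allocated equally to the arms, again with stratification "based on the day of the week the upcoming visit is on to minimize logistic difficulties in the intervention delivery". Section 5.6 adds: "The active interventions in Aim 1 are expected to last no more than 1 week", without saying whether this is per patient or for the whole trial.

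Section 6.4 states: "Sample size estimates suggest that ~1,100 individuals in each arm will allow us to observe a 5% difference in vaccination rates", with 20% under usual care, alpha 0.05 and power 0.80. It also says: "we expect to identify at least 5,000 patients who have not yet received the booster vaccination at the outset of the trial". It gives no ICC, number of days, patients per day or design effect.

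The primary analysis in section 6.5.1 is: "We will use logistic regression to compare outcomes between each intervention arm versus usual care and against each other". Section 6.5.2 repeats this for the 6-week outcome and adds only adjustment for imbalanced baseline characteristics. No random effect, GEE, cluster-robust variance or cluster-level test appears anywhere in the plan.

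**The concern.** Patients seen on the same day can share clinicians, session type, staffing and that day's news. The primary outcome is vaccination at the visit itself, so these are plausible common causes. When whole days are allocated, the variation between days goes into the arm comparison. Ordinary logistic regression does not count it, so p-values are too small and intervals too narrow. Stratifying by clinic does not remove day-to-day variation within a clinic, and clinic is not in the stated model.

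There are two consequences. The type I error is the firmer one, because recruiting more patients does not remove it. The loss of power is conditional, because the expected number of patients exceeds the calculated requirement. The 6-week outcome counts vaccination at any location and is probably less affected.

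The unit is also unclear. It could be each calendar visit date or a weekday assigned once, and it could be shared across clinics or drawn within clinic. The number of independent units, and so what any analysis can support, depends on which is meant.

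**Working it through.** **Inputs from the plan (6.4).** Usual care 20%, intervention 25%, alpha 0.05 (taken as two-sided, which reproduces the figure), power 0.80, ~1,100 per arm, at least 5,000 patients in total (5,000/3 = 1,667 per arm). For the 6-week outcome: usual care 25% and a detectable difference below 6 points.

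**Inputs assumed.** Patients per randomised unit (m) and the within-unit ICC. The documents give neither.

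**Step 1: the plan's own figure.** The pooled two-proportion formula is n = [1.96·√(2·p̄(1−p̄)) + 0.842·√(p₁(1−p₁)+p₂(1−p₂))]² / (p₂−p₁)². With 0.20, 0.25 and p̄ = 0.225, n = 1,094 per arm. Power is 80.2% at 1,100 and 93.3% at 1,667. The stated ~1,100 is therefore the independent-patient figure, with a design effect of 1.

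**Step 2: allowing for clustering.**
- Design effect: DE = 1 + (m−1)·ICC.
- Type I error of the unadjusted test: 2·[1 − Φ(1.96/√DE)].
- Power of a valid test: the step 1 formula at n/DE.

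Worked example, m = 20 and ICC 0.05: DE = 1 + 19 × 0.05 = 1.95; 1.96/√1.95 = 1.404; type I error 16.0%. At 1,100 per arm the effective size is 1,100/1.95 = 564, with 52% power.

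| m | ICC | DE | Type I error | Power at 1,100 | Power at 1,667, same m | Power at 1,667, same number of units |
|---|---|---|---|---|---|---|
| 5 | 0.01–0.05 | 1.04–1.20 | 5.5–7.4% | 79–73% | 92–88% | 92–85% |
| 20 | 0.01–0.05 | 1.19–1.95 | 7.2–16.0% | 73–52% | 89–70% | 86–60% |
| 55 | 0.005–0.02 | 1.27–2.08 | 8.2–17.4% | 70–50% | 87–67% | 83–57% |

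In the last column m grows by 1,667/1,100 = 1.515. At the low end, m = 10 and ICC 0.001 give DE 1.009, type I error 5.1% and power 80%.

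Beta-binomial simulation (20,000 runs, 1,100 per arm, unadjusted logistic Wald test) agrees: 5.3% and 7.0% at m = 5; 7.0% and 16.1% at m = 20; 8.3%, 11.2% and 17.4% at m = 55 (ICC 0.005, 0.01, 0.02). A cluster-level t-test held 4.7–5.3% throughout.

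**Step 3: how far 5,000 patients carry the plan.** The tolerable DE for 80% power is 1,667/1,094 = 1.52, which is ICC 0.13, 0.028 or 0.0097 at m = 5, 20 or 55. At that DE the unadjusted test runs at 11.2%.

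**Step 4: 6-week outcome.** 25% vs 31% needs 878 per arm. The claim tolerates DE 1,100/878 = 1.25 at 1,100 per arm and 1,667/878 = 1.90 at 1,667.

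**Step 5: the extreme reading.** Suppose five weekdays are assigned once across all clinics, with 1,000 patients each. The sampling variance of a weekday's rate is 0.20 × 0.80/1,000 = 0.00016. A true weekday SD of 1 point adds 0.0001, so the variance ratio is 1.625 and the type I error about 12%. An SD of 2 points adds 0.0004, giving ratio 3.5 and about 29%. Simulation with weekdays split 2/2/1 (200,000 runs) gives 12.3% and 29.3%, and 6.8% at an SD of 0.5 points.

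**The case against.** The strongest reply concerns size. The ICC may be close to zero. If days are drawn within clinic, clusters are small and only correlation beyond clinic differences matters. At m = 10 and ICC 0.001 the inflation is negligible. That is right, and it means the documents cannot fix the magnitude. It does not justify assuming zero without saying so, and if the ICC is negligible a clustered analysis with enough units costs almost nothing.

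Second, the five-unit case is the less likely reading. Section 4.3 describes a rolling process that looks 2–3 days ahead each weekday, and the one-week statement in section 5.6 reads naturally as per patient. This largely stands: the 12% and 29% figures apply only if weekdays really were assigned once. The literal wording of section 4.3 still allows it, so the text should exclude it. The figure in 5.2.1 and the schema in 5.3 are not visible in the copy reviewed and might clarify the unit. They are unlikely to supply an analysis method.

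Third, the plan takes all eligible patients, so power has reserve, including a 6-week tolerance of 1.90 at 5,000 patients. This stands for power only.

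Fourth, this is called a pilot, and naming logistic regression does not rule out robust standard errors. But the trial is powered and tested at alpha 0.05, and the analysis as written specifies nothing beyond the plain model.

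**Conclusion.** The concern holds. Section 4.3 defines a cluster-randomised trial, while sections 6.4, 6.5.1 and 6.5.2 size and analyse it as if patients were independent. Followed as written, the analysis does not assure a 5% error rate whenever same-day outcomes correlate. For the cluster sizes and ICCs assumed here (5 to 55 per unit, ICC 0.005 to 0.05), the type I error is about 5.5% to 17%. It is close to 5% when both are very small, and exactly nominal in this approximation at ICC 0. Power at 1,100 per arm falls to between 79% and 50% over the same range. With 5,000 patients it stays at 80% up to a design effect of about 1.52. The omission and the conflict between sections are certain from the text; the magnitude is illustrative. This should be corrected before the primary comparison is relied on.

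**What to change.** 1. **Sections 4.3, 5.2, 5.2.1 and 5.6.** State what was randomised: calendar visit date or weekday assigned once; shared across clinics or drawn within clinic; and whether weekday is also a stratum. Reconcile the wording that has patients being randomised. Say whether the one-week limit is per patient or trial-wide.
2. **Sections 6.5.1 and 6.5.2.** Use a logistic GEE or mixed model clustered on that unit, with small-sample-corrected standard errors and clinic (and weekday, if a stratum) as covariates. If weekdays were assigned only once, clusters may be too few and arm is partly confounded with weekday. No model repairs that, and the conclusions must say so.
3. **Section 6.4.** State an ICC range and the expected number and size of clusters. Restate power or detectable difference at 1,100 and about 1,667 per arm for both outcomes.

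The cost is wording in seven sections and a different model call. Visit day and clinic are already known from the allocation. Intervals will widen and stated power may fall below 80% even with 5,000 patients. At 55 per unit, 80% power needs 3 × 1,094 × 1.54, about 5,050 patients, at ICC 0.01, and 3 × 1,094 × 2.08, about 6,830, at ICC 0.02. The plan would then have to accept a larger detectable difference (from 20%, at 1,667 per arm and 55 per unit, 4.6 to 5.9 points over ICC 0.005 to 0.02) or recruit for longer.

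### Weekday of visit is named both as the randomised unit and as a stratum, with no block schedule, so balance over weekdays and calendar time is not secured

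*Combined protocol and SAP*

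**What the plan says.** Section 4.3 introduces the scheme with "We will also use block-stratified randomization" and then says that "the unit of randomization is the day of the week the study visit is on". The mechanism is rolling: "Each weekday, eligible patients will be identified that have an upcoming visit 2-3 days from then", after which "The day of the week of that visit will be randomized in a 1:1:1 ratio with a random number generator". The section also announces stratification by clinic.

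Section 5.2 gives weekday a different role: "We will conduct stratified randomization based on the primary care clinic the patient attends and day of the week the upcoming visit is on". Section 5.2.1 repeats weekday as a stratum, "based on the day of the week the upcoming visit is on to minimize logistic difficulties in the intervention delivery", and describes patients as being randomised in equal numbers to the arms. Section 5.6 adds: "The active interventions in Aim 1 are expected to last no more than 1 week".

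The following are not stated anywhere:
- whether a weekday is assigned once or each calendar date is drawn afresh;
- whether one draw covers all clinics;
- block size, block period or schedule;
- the number of clinics and the length of enrolment.

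Section 6.5.1 plans logistic regression for the arm comparisons and names no term for clinic, weekday or calendar time. Section 6.5.2 mentions adjustment for imbalanced baseline characteristics, in secondary analyses only.

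**The concern.** A stratum is a set of units within which the arms are balanced. If the weekday is itself the unit, nothing is left inside the stratum to balance. The reason given in 5.2.1 points to the source of the confusion: assigning a whole day to one arm makes delivery easier, whereas stratifying by day does not.

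The ambiguity matters because patients seen on different weekdays may differ, and booster uptake among people not yet boosted may drift during enrolment. If arms are spread unevenly over weekdays or weeks, those differences enter the arm contrast. Nor could a statistician generate the allocation list, or repeat it later, from the present text. Whether the analysis allows for clustering by day is a separate matter and is not argued here.

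**Working it through.** **The plan's own figure.** Section 6.4 gives about 1,100 per arm for 20% against 25%, alpha 0.05, power 0.80. The two-sided two-proportion formula with pooled variance gives 1,094, and power at 1,100 per arm is 0.802. The figure reproduces. At that size the sampling SE of an arm difference is √[(0.20 × 0.80 + 0.25 × 0.75)/1,100] = 1.78 points, which is the yardstick below.

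**Reading A: each weekday is assigned once.** Five units cannot be split 1:1:1; the nearest split is 2:2:1. Each weekday then sits in one arm only, so weekday and arm cannot be separated within whatever the draw covers (all clinics, or each clinic). With one independent draw per weekday for all clinics, the chance that an arm gets no weekday is (3 × 2⁵ − 3)/3⁵ = 93/243 = 38.3%. With 5 clinics drawn separately (25 draws) it is about 3 × (2/3)²⁵ = 0.01%, but the confounding within each clinic remains. If the one-week statement in 5.6 refers to the whole trial, each weekday occurs only once and this reading is forced.

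**Reading B: each calendar date is drawn independently.** Assume 6 weeks, 30 dates and equal daily volume.

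*Weekday coverage.* The chance that at least one weekday never receives some arm is 1 − [1 − (3 × 2^k − 3)/3^k]⁵, where k is the number of draws per weekday.
- One draw per date for all clinics, k = 6: 1 − (1 − 189/729)⁵ = 77.7%. At 12 weeks it is 11.0%.
- Five clinics drawn separately, pooled, k = 30: about 5 × 3 × (2/3)³⁰ = 0.008%. Within any one clinic it is still 77.7%.

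*Calendar time.* With one draw per date for all clinics, the share of an arm's days in the first half of enrolment differs by 20 points or more between two arms in 67% of simulated draws at 6 weeks and 43% at 12 weeks.

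*Effect on the arm difference.* Assume weekday effects with SD 2 points and a linear 5-point drift over the 30 dates, both the same in all clinics.
- Weekday variance about the mean of five days: 4 × 4/5 = 3.2.
- Drift variance: 25 × (30² − 1)/(12 × 29²) = 2.23.
- Independent draws, one for all clinics, 10 dates per arm: √[(3.2 + 2.23) × (2/10) × (30/29)] = 1.06. Unequal date counts raise this to 1.10 in simulation.
- C clinics drawn separately: divide by √C. Simulation gives 0.47 for 5 clinics and 0.33 for 10.

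*With permuted blocks of three same-weekday dates.* Weekday cancels. The drift per week is 5 × 5/29 = 0.862. Two arms in a block are 1, 1 or 2 weeks apart with equal chance, so the mean squared gap is (1 + 1 + 4)/3 = 2. With 10 blocks the SD is √(2 × 0.862²/10) = 0.39 (0.38 in simulation).

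| Draw | Independent | Blocked |
|---|---|---|
| One for all clinics | 1.10 | 0.38 |
| 5 clinics separately | 0.47 | 0.17 |
| 10 clinics separately | 0.33 | 0.12 |

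Added in quadrature to 1.78, the independent-draw values give 2.09, 1.84 and 1.81 points, an SE about 18%, 3% and 2% larger.

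**The case against.** The strongest reply is that the wording in 4.3 is compatible with a sound design: calendar date as unit, clinic and weekday as strata, blocks running over weeks. A random number generator can produce permuted blocks, and the text never says that draws are independent. This stands. The defect is under-specification and contradiction; a reader who infers that the scheme rules out balance goes further than the documents allow.

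Second, all three design sections stratify by clinic. If that means separate draws per clinic, most of the imbalance averages out over clinics, as the table shows. This also stands, and it is why the figures for a single draw covering all clinics must not be read as the expected case.

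Third, a reader might infer that an arm below 1,100 loses the planned power. It need not. Of 5,000 patients, a 2:2:1 split gives 2,000, 2,000 and 1,000. A contrast of 2,000 with 1,000 is equivalent to 2/(1/2,000 + 1/1,000) = 1,333 per arm, with power 0.87 under the plan's own formula, above the planned 0.80. Section 6.4 also gives 5,000 as a minimum. The shortfall argument is not part of this point.

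What the reply does not remove is that the unit, the strata and the block must be written down consistently, and that the primary model names nothing to absorb imbalance that does occur.

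**Conclusion.** The contradiction between 4.3 and sections 5.2 and 5.2.1 is real and should be resolved. Under the assumed weekday SD, drift and 6-week enrolment, independent date draws give a chance arm difference with SD about 1.1 points if one draw covers all clinics and 0.3 to 0.5 points with 5 to 10 clinics drawn separately, against a target difference of 5 points. Blocking reduces each about threefold. None of these inputs is in the documents: weekday spread, drift, number of clinics and enrolment length are all assumed, and longer enrolment or more clinics makes the effect smaller.

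A reader might also infer systematic bias. Independent draws are unbiased in expectation, so under Reading B the cost is chance imbalance and precision. Under Reading A the realised contrast is tied to particular weekdays, at least within clinic. Nothing here shows that the trial as run was unbalanced. The point merits correction because the remedy is cheap, but it does not by itself undermine the trial.

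**What to change.** - **4.3:** define the unit as clinic by calendar visit date, with clinic and weekday as strata. Within each clinic and weekday, assign successive same-weekday dates from a pre-generated permuted-block list, three dates per block, one per arm. Each weekday in each clinic then receives every arm once every three weeks.
- **5.2 and 5.2.1:** use the same definitions, and state that dates within clinic, not individual patients, are randomised.
- **6.5.1:** include clinic, weekday and calendar period in the primary logistic model.
- **5.6:** say whether the one-week duration is per patient or for the trial.

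The cost is a pre-generated clinic-by-date list in place of a daily draw, and enrolment preferably in whole three-week blocks. Delivery becomes somewhat harder, because clinics may be in different arms on the same date; this bears on the logistical reason that 4.3 gives for randomising by day. Small blocks make some dates predictable, which matters little when eligibility is set by a data query.
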